### **8.4 Imaging and cardiac studies**

- Chest xray (posteroanterior and lateral): findings must not be consistent with infiltrate, pulmonary malignancy, heart failure, or respiratory disease.
- 12-lead EKG: findings must not be consistent with ischemia or prior infarction, left ventricular hypertrophy, delayed conduction, prolonged QT (>450ms in male or >460ms in female), or serious arrhythmias.

### **8.5 Microbiome analyses**

Stool for microbiome analysis will be collected at screening visit and weeks 0, 2, 4, 6, 8, 10, 12, 16, 20, 24, 36 or early termination. Microbial community structure will be analyzed from stored fecal samples collected in each patient group. Samples will be kept at -80 C until DNA extraction. The V4 region of the 16S rRNA gene will be PCR amplified in triplicate, and the resulting amplicons cleaned, quantified and sequenced on the Illumina MiSeq platform using custom barcoded primers. Raw sequences will be processed using the QIIME software package (Quantitative Insights Into Microbial Ecology; <http://qiime.org/>). Only full-length, high-quality reads will be used for analysis. OTUs are picked at 97% similarity against the Greengenes database. Subsequent analysis of 16S rRNA data will include weighted and un-weighted UniFrac distance matrix, and calculations of  $\alpha$  and  $\beta$  diversity.

### **8.6 Transcriptomics analyses**

Serum metabolites and colonic mucosa will be obtained at Screen, week 12, and week 24 Blood and colonic mucosa (screening, week 12, week 36) will be collected for analyzing serum metabolites and RNAseq to determine treatment-related changes in gene expression (transcriptomics).

## **9 Statistical Plan**

### **9.1 Sample Size Determination**

The primary endpoint is endoscopic response, defined as a 50% reduction SES-CD scores at week 12. We will assume a placebo response rate of 10%, and a treatment response rate of 70%. Therefore, with a study size of 24 patients (11 in each group, plus 2 potential dropouts before the second colonoscopy) there will be 76% power in a Fisher's Exact test with a target

alpha of 0.05. The significance level actually achieved with binomial enumeration is 0.002. (Power estimates computed with PASS2020 software).

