| Transcriptomics Endpoints           | 
 
Changes in stool and mucosal washing metabolites
 
Changes in microbiome / metabolome reflected in gene expression patterns in mucosal biopsies
 
  |

|                                    |  |
|------------------------------------|--|
| 
Statistical
Methodology
 | 
The primary analysis population will be the intention-to-treat population. The primary efficacy endpoint and key secondary endpoints will also be analyzed with the per-protocol population. The primary and key secondary endpoints will be evaluated using descriptive statistics, Exact Fisher's and t-test to compare treated vs placebo-controlled subjects. . In the case of missing clinical data, the missing data points will be treated by non-responder imputation.
 
The primary endpoint is endoscopic response, defined as a 50% reduction SES-CD scores at week 12. Each patient will be scored on a binary response (improved/not improved). We will assume the placebo response rate of approximately 10% . We estimate that a study size of 24 patients is necessary, assuming a drop-off rate of ~10% before the second colonoscopy, to yield final analysis of at least 11 subjects per arm. With a final sample size of 22 subjects, we will have 76% power to detect a difference of 0.50 in the rate of response for treatment with posaconazole therapy vs placebo from the assumed underlying placebo response rate at the 0.05 significance level in a Fisher's Exact Test. This assumes the treatment response rate will be 0.70h or greater.
 
Secondary endpoints will include clinical remission (defined as Crohn's disease activity index < 150), analysis of data regarding use of corticosteroids, mucosal healing, mucosal improvement, normalization of inflammatory biomarkers, and improvement in health-related quality of life. Repeated measures analysis will be used to examine changes over time from baseline. Categorical data will be analyzed with repeated measures logistic regression while continuous measures will use mixed modeling regression. Residuals will be inspected to confirm data meets assumptions necessary for parametric testing. Data will be considered significant at the two-sided p-value of <0.05. All analysis will be performed by the study biostatistician ([name], MS) using SAS v9.4 software.
 |
|------------------------------------|--|

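### The 76% power is for 22 completers; for the ITT, non-responder-imputed primary analysis it is about 73% to 75% if 10% and 70% are completer rates, and 11 per arm is not assured

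*Combined protocol and SAP*

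**What the plan says.** Section 9.1 gives the size as 24 patients: "11 in each group, plus 2 potential dropouts before the second colonoscopy". Its assumptions, in per cent, are "We will assume a placebo response rate of 10" and "a treatment response rate of 70". It concludes that "there will be 76% power in a Fisher's Exact test with a target" alpha of 0.05. The synopsis (Statistical Methodology) ties the same power to the reduced number: "With a final sample size of 22 subjects, we will have 76% power to detect a difference of 0.50". It reaches 22 by "assuming a drop-off rate of ~10% before the second colonoscopy, to yield final analysis of at least 11 subjects per arm".

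The same synopsis entry sets the analysis: "The primary analysis population will be the intention-to-treat population", and "In the case of missing clinical data, the missing data points will be treated by non-responder imputation". Section 9.3 defines ITT as everyone who took at least one dose, and Section 6.3 has the first dose observed at the baseline visit. Section 9 does not repeat the imputation rule, and neither place names the Week 12 SES-CD as covered by it. No power is given for an analysis of all 24.

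**The concern.** The sample-size text removes dropouts and then tests 70% against 10% in those who remain. The primary analysis does not remove them. A dosed subject without a Week 12 score is counted as a non-responder, which lowers the observed response rate in both arms while the denominators stay at 12. The stated power therefore belongs to a completer analysis, not to the analysis named as primary.

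The synopsis also presents 11 per arm as a minimum. Its own drop-off rate does not deliver that as an expected total, and random losses need not fall one in each arm. This paragraph is the main quantitative justification for 24 subjects, so readers will take the power and the per-arm count as properties of the reported result.

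**Working it through.** **Inputs.** 24 subjects, 1:1 (Section 5, opening paragraph), taken as 12 + 12; response rates 10% and 70% (Section 9.1); two-sided 0.05 (Section 9.2); Fisher's exact test; drop-off of 2 of 24 = 8.3% (Section 9.1) or about 10% (synopsis).

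**Formula.** Power = Σ over a, b of Bin(a; n₁, p₁) × Bin(b; n₂, p₂), summed over the outcomes with a two-sided Fisher p-value of at most 0.05.

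**Step 1: reproduce the plan.** With n₁ = n₂ = 11 and rates 0.70 and 0.10, power is 75.5%, which rounds to 76%. The achieved size at a common rate of 10% is 0.0017, matching the 0.002 in Section 9.1. The stated figure is right for its stated inputs.

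**Step 2: power for the primary analysis.** Assume 10% and 70% are completer rates, and that drop-off d is equal in both arms and unrelated to response. Under non-responder imputation the observed rates become p × (1 − d), with 12 per arm:

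| Drop-off | Posaconazole rate | Placebo rate | Power |
|---|---|---|---|
| 0 | 0.700 | 0.100 | 82.6% |
| 2/24 | 0.70 × 22/24 = 0.642 | 0.10 × 22/24 = 0.092 | 74.4% |
| 10% | 0.70 × 0.90 = 0.63 | 0.10 × 0.90 = 0.09 | 72.6% |

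**Step 3: exactly two dropouts, still analysed as 12 + 12.**

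| Where the two fall | Probability | Power |
|---|---|---|
| One in each arm | 144/276 = 0.522 | 75.5% |
| Both on posaconazole | 66/276 = 0.239 | 61.5% |
| Both on placebo | 66/276 = 0.239 | 85.9% |

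The average is 0.522 × 75.5 + 0.239 × 61.5 + 0.239 × 85.9 = 74.6%.

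**Step 4: the minimum of 11 per arm.** 24 × 0.90 = 21.6, which is below 22. An arm of 12 keeps at least 11 if it loses none or one:

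- At 10%: 0.9¹² + 12 × 0.1 × 0.9¹¹ = 0.659 per arm; both arms, 0.659² = 0.43.
- At 2/24: (11/12)¹² + (11/12)¹¹ = 0.736 per arm; both arms, 0.736² = 0.54.

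**Step 5: the other reading of the rates.** If 10% and 70% already count dropouts as failures, imputation must not be applied a second time, and 12 + 12 gives 82.6%.

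**Step 6: the stated difference.** The synopsis names a difference of 0.50 beside rates of 10% and 0.70, but 0.70 − 0.10 = 0.60. With 11 per arm, 10% versus 60% gives 55.9%, and 20% versus 70% about 52%. Of these pairs, only 10% versus 70% matches 76%.

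**The case against.** The case on the other side is substantial.

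- **There is no arithmetic error.** This stands. The 76% reproduces; the question is which analysis it describes.
- **On the plan's literal scenario nothing changes.** With one dropout per arm the imputed analysis has 75.5%, the same as the completer analysis, and averaging over all placements of two dropouts costs about one point. This also stands. The 73% needs a full 10% drop-off, or 2.4 expected losses.
- **The rates may already be ITT rates.** The placebo rate comes from cited trials that cannot be checked here. On that reading 76% understates the power. Applying the rates to 22 remaining subjects favours the completer reading, but the plan does not settle it.
- **Imputation of the SES-CD is inferred.** The rule refers only to clinical data and appears only in the synopsis. Table 1 (footnote 1) and Section 7.4 also send early discontinuers through the Week 12 procedures, so some withdrawals may still yield a score. Against this, the rule sits beside the primary-endpoint analysis, and the dropouts used for sizing are by definition lost before the second colonoscopy.
- **Uneven losses do not hurt a completer analysis.** Correct: 10 on posaconazole and 12 on placebo gives 79.0%, and the reverse gives 84.3%. Missing the 11-per-arm minimum is an inaccurate statement, not a loss of completer power.

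A reader might infer that the trial is materially underpowered, or that its true power is nearer 61%. The documents do not support this. The 61.5% needs both dropouts on posaconazole, which is exactly as likely as both on placebo (85.9%).

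**Conclusion.** The point holds at minor severity. The stated 76% (75.5% exactly) is a completer figure for 11 per arm, while the named primary analysis is ITT with non-responder imputation. For that analysis power is about 74% to 75% with 2 of 24 lost and about 73% at 10% drop-off, so the overstatement is roughly one to three points.

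This rests on four assumptions: 10% and 70% are completer rates; imputation covers a missing Week 12 SES-CD; drop-off is equal across arms and unrelated to response; and allocation gives 12 + 12. The plan states 1:1 randomisation through REDCap but describes no blocking. If the first assumption fails because the rates already include dropouts as failures, power is 82.6% and the stated figure is conservative.

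Separately from the power, the minimum of 11 per arm is not assured at either drop-off figure in the plan (43% or 54%).

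**What to change.** In Section 9.1 and the synopsis:

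1. Say that 10% and 70% are rates among subjects with a Week 12 endoscopy, if that is what is meant, and that a missing Week 12 SES-CD counts as non-response. Put the imputation rule in Section 9 as well.
2. State power for the primary analysis: about 73% with 12 randomised per arm, about 10% missing, and two-sided Fisher at 0.05. Keep 76% as the supportive figure for 11 completers per arm.
3. Replace the minimum of 11 per arm with an expected total of about 21 to 22 subjects with Week 12 endoscopy.
4. Reconcile the difference of 0.50 in the synopsis with 10% versus 70%, which is 0.60.

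The cost is a few sentences and a slightly less favourable stated power. Neither the number of patients nor the planned test changes. If the sponsor instead confirms that the rates already count dropouts as failures, item 1 should say so and item 2 should give 82.6%.

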# **5 Subject Selection and Withdrawal**

Subjects (n=24) will be individuals with active Crohn's disease (SES-CD  $\geq 6$  AND PRO2 score of abdominal pain  $\geq 2$  OR PRO2 daily stool frequency  $\geq 4$ ) despite use of conventional therapy. Subjects will be randomly assigned to receive posaconazole or placebo in 1:1 fashion. In this 40-week trial, subjects assigned to treatment will be administered posaconazole (Noxifil®, Merck) 300mg daily for 12 weeks. and then observed off posaconazole over the next 24 weeks. In addition to the treatment intervention, subjects also will provide samples for parallel translational studies including blood for genetic analysis, stool samples for biomarker and microbial composition analysis, and biopsies for mucosal gene expression analysis. Patients meeting criteria for active disease at 12 weeks will be offered open-label posaconazole for 12 weeks and will continue all study-related visits and procedures until final safety visit at week 36.

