## **5.1 Randomization**

At the baseline visit, subjects will be randomized via REDCap to receive posaconazole or placebo.

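### The synopsis ties 76% power to a 0.50 difference, but it belongs to 0.60; separately, an unconditional exact test is an optional gain of roughly 0 to 10 power points

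*Combined protocol and SAP*

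**What the plan says.** Section 9.1 assumes response rates of 10% on placebo and 70% on posaconazole. It plans for 24 patients, leaving 11 per group after two possible dropouts, and states that "there will be 76% power in a Fisher's Exact test with a target" alpha of 0.05. It adds: "The significance level actually achieved with binomial enumeration is 0.002". Section 9.2 makes significance two-sided at 0.05.

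The synopsis (Statistical Methodology) uses the same numbers of patients and a placebo rate of about 10%, but says "we will have 76% power to detect a difference of 0.50 in the rate of response". The same paragraph ends by assuming a treatment rate of at least 0.70.

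On the analysis set, the synopsis says "The primary analysis population will be the intention-to-treat population", and for missing clinical data "the missing data points will be treated by non-responder imputation". It also sizes the trial "to yield final analysis of at least 11 subjects per arm", which reads like a completer count.

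On allocation, section 5 says "Subjects will be randomly assigned to receive posaconazole or placebo in 1:1 fashion" and section 5.1 says "subjects will be randomized via REDCap to receive posaconazole or placebo". Neither these sections nor section 7.2 mentions blocking. Section 7.4 unblinds each subject after the week-12 evaluations. No unconditional exact test is mentioned anywhere.

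**The concern.** Two separate things stand out.

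The first is a contradiction. The synopsis gives one power figure for a 0.50 difference, and section 9.1 gives the same figure for a 0.60 difference. Both cannot hold with 11 per arm. A reader of the synopsis alone would believe that the trial has about three chances in four of detecting a 50-point effect.

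The second is efficiency. Section 9.1 itself prints an achieved level far below its 0.05 target. In a 24-patient trial, a test that uses more of the permitted error can find the same effect more often without more patients. What is at stake is the chance of missing a true 70% against 10% effect, and how far that chance can be cut depends on arm balance, missing outcomes and the exact definition of the test.

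**Working it through.** **Inputs from the documents:** rates 0.70 and 0.10, 11 per arm, 24 enrolled, two dropouts, Fisher's exact test, alpha 0.05 (section 9.1); two-sided (section 9.2); ITT with non-responder imputation (synopsis). **My assumptions:** the dropout patterns below, and that imputation covers a missing week-12 endoscopy.

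**Method.** Power is the sum, over all tables (a responders on posaconazole, b on placebo) that the test rejects, of Bin(a; n1, p1) × Bin(b; n2, p2).

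**Step 1: reproduce the plan's figure.** At 11/11, two-sided Fisher rejects in favour of posaconazole when a is at least 5, 7, 8, 9, 10, 11, 11 for b = 0, 1, 2, 3, 4, 5, 6. At 70% against 10%:

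- b = 0: 0.3138 × 0.9784 = 0.3070
- b = 1: 0.3835 × 0.7897 = 0.3029
- b = 2: 0.2131 × 0.5696 = 0.1214
- b = 3: 0.0710 × 0.3127 = 0.0222
- b = 4: 0.0158 × 0.1130 = 0.0018
- other terms: below 0.0001

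The sum is 0.7553, which rounds to the stated 76%. The error rate when both arms respond at 10% is 0.0017, which matches the printed 0.002.

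**Step 2: a 0.50 difference.** With a placebo rate of 10%, the treated rate is 60%. The tail probabilities for the first five lines become 0.9006, 0.5328, 0.2963, 0.1189 and 0.0302. The products are 0.2826 + 0.2043 + 0.0631 + 0.0084 + 0.0005 = 0.559. Power is 55.9%, not 76%.

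**Step 3: how conservative Fisher is.** I maximised the two-sided error over all common response rates. Boschloo here takes the two-sided Fisher p as its statistic and maximises over the common rate.

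| Arms | Fisher, worst case | Boschloo, worst case |
|---|---|---|
| 11/11 | 0.017 | 0.040 |
| 12/12 | 0.023 | 0.045 |

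At both sizes Boschloo keeps every Fisher rejection. At 11/11 it adds 6-1, 7-2, 9-4 and 10-5 (and mirror images). For 6-1, Fisher p is 0.064 and Boschloo p is 0.026. The added power is 0.3835 × 0.1321 + 0.2131 × 0.2201 + 0.0158 × 0.1998 + 0.0025 × 0.0932 = 0.0507 + 0.0469 + 0.0032 + 0.0002 = 0.1010, so power is 0.7553 + 0.1010 = 0.8563.

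**Step 4: the gain in other settings, 70% against 10%** (arms are posaconazole/placebo).

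| Setting | Fisher | Boschloo | Gain (points) |
|---|---|---|---|
| 11/11 evaluable | 75.5% | 85.6% | 10.1 |
| ITT 12/12, two imputed non-responders at random | 74.6% | 85.1% | 10.4 |
| 12/12, no missing outcomes | 82.6% | 89.5% | 6.9 |
| ITT 24 unblocked, each drops out with chance 1/12, imputed | 76.6% | 83.4% | 6.8 |
| 24 unblocked, no missing outcomes | 84.0% | 88.4% | 4.4 |
| Completers 10/12 | 79.0% | 82.9% | 3.9 |
| Completers 12/10 | 84.3% | 84.3% | 0.0 |

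The gains come from unrounded powers. If the one-sided Boschloo p is doubled instead, the unblocked ITT row becomes 81.4% (gain 4.8) and 12/10 becomes 85.7%. At 11/11 and 12/12 the two definitions reject the same tables.

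**Step 5: the price.** Given the total number of responders, Boschloo's error can exceed 0.05. At 11/11 it is 0.063 at totals of 7 or 15 and 0.081 at 9 or 13; under the plan's rates one of these totals occurs 37% of the time. At 12/12 it is 0.069 at 7 or 17, 0.089 at 9 or 15, and 0.093 at 4 or 20. A 4-0 split at 12/12 (Fisher p 0.093) becomes significant (Boschloo p 0.045).

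**The case against.** Fisher's exact test is standard, valid and named in advance. Both printed figures reproduce, and section 9.1 discloses the achieved level openly. Choosing between conditional and unconditional error control is a judgement, and a team that wants conditional control has a sound reason to keep Fisher. All of this stands, and it is why the change of test is only an option.

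The gain is also easy to overstate. The 10-point figure needs equal arms and either 11 evaluable per arm or two outcomes counted as failures. Table 1 (footnote 1) asks early discontinuers to undergo the week-12 procedures, which include colonoscopy, so a dropout need not have a missing outcome. With no missing outcomes the gain is 6.9 points at 12/12 and 4.4 unblocked. For 12/10 completers it disappears.

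Nor does a better test cure a large assumed effect. At 11/11 and 40% against 10% (my assumption), power goes only from 19.1% to 26.3%.

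A reader might infer from the printed 0.002 that Fisher was misapplied, or that Boschloo recovers the unused error. Neither follows. The 0.002 is the error at a common 10% rate, where Boschloo at 11/11 also spends only 0.0020.

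None of these arguments touches the 0.50 figure, which is inconsistent whichever test is used.

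**Conclusion.** **Wrong as written:** the synopsis's 0.50. The 76% belongs to 70% against 10%, a difference of 0.60; at 60% against 10% with 11 per arm Fisher's power is 55.9%. A reader might go further and infer that the trial was really sized for 0.50 and is underpowered against its own target. The documents do not support that: section 9.1 states 70%, and the synopsis paragraph itself ends with 0.70. This is a misstatement of the difference, not evidence of a different design.

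**Optional improvement:** two-sided Boschloo at the same 0.05 limit. At 70% against 10% the gain is roughly 0 to 10 points: about 10 at 11/11 or at ITT 12/12 with two imputed non-responders, 6.9 at 12/12 with nothing missing, about 5 to 7 unblocked with imputed dropouts depending on the definition, 4.4 unblocked with nothing missing, and about 0 to 4 for unbalanced completers. In the favourable ITT 12/12 case, the chance of missing the effect falls from about 25% to 15%. A reader might take ten points as assured; the documents do not secure the balance or the missing-data pattern that this needs.

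**What to change.** 1. **Correct the synopsis.** Change the difference to 0.60, or keep 0.50 and state power of about 56% (60% against 10%, 11 per arm). This costs one line and is needed whatever test is used.

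2. **Optional, and only before the first week-12 unblinding.** Name two-sided Boschloo at 0.05 as the single primary test of endoscopic response in the synopsis and sections 9.1 and 9.2, with Fisher's p-value as supportive. Write down the two-sided definition (two-sided Fisher p as the statistic, maximised over the common rate) and the software. Say that error control is unconditional only. Restate power for that test on the ITT set.

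3. **With either test,** state whether REDCap allocation is blocked, because the size of the gain depends on balance.

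4. **If any subject has already been unblinded,** keep Fisher primary and report Boschloo as supportive only. The documents do not give enrolment status.

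The cost of item 2 is plan wording and a short program. The plan names SAS v9.4; whether this definition runs there has not been shown, so checked enumeration code should be archived alongside it. The other costs are a less familiar test, conditional error up to about 0.08 at 11/11 and 0.09 at 12/12, and having to defend a 4-0 result as significant at 12/12.

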- Sample size: 12 patients will be recruited for this open-label pilot study. Given the pilot nature of this study, a sample size justification is not provided.

## 9.3 Subject Population(s) for Analysis

- Intention-to-treat (ITT) population: All subjects in the study who received at least one dose of study drug
- Per-protocol population: All subjects in the study who received the protocol-required study drug

## 10 Safety and Adverse Events

### 10.1 Recording of Adverse Events

At each contact with the subject, the investigator must seek information on adverse events by specific questioning and, as appropriate, by examination. Information on all adverse events should be recorded immediately in the source document. All clearly related signs, symptoms, and abnormal diagnostic procedures results should be recorded in the source document, though should be grouped under one diagnosis.

All adverse events occurring during the study period will be recorded. The clinical course of each event should be followed until resolution, stabilization, or until it has been determined that the study treatment or participation is not the cause. Serious adverse events that are still ongoing at the end of the study period must be followed up to determine the final outcome. Any serious adverse event that occurs after the study period and is considered to be possibly related to the study treatment or study participation should be recorded and reported immediately.

